3.2.2.1.1 Study periods for safety data

The following study periods are defined for the classification of safety data by study period:

- Pre-treatment Period (Screening Period): Starts at the time of the informed consent date and ends prior to the day and time of the first dose administration of study drug.
- 16-Week Double-Blind Treatment Period (DBTP): Starts on the day of the first IMP administration and ends prior to the day of first IMP administration in the maintenance period (first IMP in the MP typically occurs at Week 16, but for those that miss the Week 16 IMP, first IMP in the MP will be the first IMP administration after Week 16). For study participants that withdraw from the study prior to start of IMP in the maintenance period, the DBTP ends on the day of the ET Visit.

See Section 3.7 (Treatment assignment and treatment groups) for allocation of AEs that occur on the day of IMP administration.

For vital sign parameters, the DBTP will start at the day and time of first IMP administration and ends prior to the day and the time of first IMP administration in the MP as there are 3 assessments collected at Baseline and Week 16 (one pre-dose, one 30 minutes post-dose and one 1-hour post-dose).

- 36-Week Maintenance Treatment Period (MP): Starts on the day of IMP administration at the Week 16 visit and ends 28 days (one dosing interval) after the day of last IMP administration before the Week 52 visit. For participants that do not receive IMP at the Week 16 visit, the MP starts on the day of first IMP administration after Week 16. For study participants that

withdraw from the study after Week 16 but before Week 52, the MP ends on the day of the ET Visit. In the event that no ET visit is performed, the MP ends 28 days after the last IMP administration.

For vital sign parameters, the day and the time will be used to define the MP for the same reason that given above.

- **Safety Follow-Up Period:** The SFU period will be defined for all study participants who complete the final IMP administration of the study at Week 48 and do not enter the OLE study, or for study participants who discontinue early including those withdrawn from IMP.
 - For study participants who complete the final IMP administration of the study at Week 48 and do not enter the OLE study, the SFU period starts 29 days after the day of last IMP administration before the Week 52 visit and ends on the day of the SFU Visit or on the last contact date, whichever happens later.

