Note: If the date of last dose + 28 extends to a date beyond the final visit date (not including SFU), then this calculation reverts to:

$$\text{Date of last visit (not including SFU)} - \text{Date of first dose} + 1$$

- For study participants who die during the DBTP, this calculation reverts to:

$$\text{Date of death} - \text{Date of first dose (DBTP)} + 1$$

- The time at risk during the DBTP will be calculated as follows:

- For study participants who complete the final visit of the DBTP and continue to the Maintenance Period:

$$\text{Date of first dose (MP)} - \text{Date of first dose (DBTP)} + 1$$

- For study participants who discontinue on or prior to the final visit of the DBTP (ie, Week 16), use the minimum of the following:

- Total number of days in the DBTP:

- For those that discontinue prior to the Week 16 visit, use 112 days,
 - For those that discontinue at the Week 16 visit, use the total number of days based on Week 16 visit date, which can be a maximum of 115 days due to visit windows

- $$\text{Date of last clinical contact} - \text{Date of first dose (DBTP)} + 1$$
, last clinical contact can be defined as last scheduled site visit.

- For study participants who die during the DBTP, then this calculation reverts to:

$$\text{Date of death} - \text{Date of first dose (DBTP)} + 1$$

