10.1.2 Duration of exposure and time at risk in the Maintenance Period

- The study medication duration during the Maintenance Period will be calculated as follows:

$$\text{Date of last dose (MP)} - \text{Date of first dose (MP)} + 28$$

- If date of last dose in the Maintenance Period + 28 days extends to a date beyond the final visit date of the Maintenance Period (not including SFU), then this calculation reverts to:

$$\text{Date of last visit (MP - not including SFU)} - \text{Date of first dose (MP)} + 1$$

- For study participants who die during the Maintenance Period, then this calculation reverts to:

$$\text{Date of death} - \text{Date of first dose (MP)} + 1$$

- For study participants who discontinue/lost to follow-up during the Maintenance Period, then this calculation reverts to:

$$\text{Date of last dose (MP)} - \text{Date of first dose (MP)} + 28$$

- The time at risk during the Maintenance Period will be calculated as follows:

- For study participants who complete the Maintenance Period as planned and continue into an open-label study (and, therefore, do not have the SFU visit in the feeder study):

$$\text{Date of last visit (MP)} - \text{Date of first dose (MP)} + 1$$

- For study participants who die during the Maintenance Period, then this calculation reverts to:

$$\text{Date of death} - \text{Date of first dose (MP)} + 1$$

- For all other study participants, use the minimum of the following:

- $$\text{Date of last dose (MP)} - \text{Date of first dose (MP)} + 140 + 1$$
 - $$\text{Date of last clinical contact} - \text{Date of first dose (MP)} + 1$$

This last group could include study participants who discontinue the Maintenance Period early, study participants who complete the Maintenance Period as scheduled but choose not to continue into an open-label study, or study participants who are ongoing in the SFU period at the time of the interim data snapshot.

Note that the Week 24 visit (ie, Visit 10) will be the last visit for the Week 24 interim analysis, and that the Week 52 visit (ie, Visit 17) will be the last visit for the Week 52 interim analysis.

10.1.3 Duration of exposure and time at risk in the combined Double-Blind Treatment and Maintenance Periods

- The study medication duration during the combined treatment period will be calculated as follows:

- For study participants who do not switch study treatments per study design:

$$\text{Date of last dose} - \text{Date of first dose} + 28$$

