- If the date of last dose + 28 days extends to a date beyond the date of the final visit date (not including SFU), then this calculation reverts to:

$$\text{Date of last visit (not including SFU)} - \text{Date of first dose} + 1$$

- For study participants who die, then this calculation reverts to:

$$\text{Date of death} - \text{Date of first dose} + 1$$

- For study participants who switch study treatments per study design (ie, study participants initially randomized to placebo who are re-allocated to bimekizumab treatment):

- During the DBTP (attributed to initially randomized treatment):

$$\text{Date of last dose (DBTP)} - \text{Date of first dose (DBTP)} + 28$$

Note: If date of last dose in the Initial Period + 28 days extends to a date beyond the date of first dose in the Maintenance Period, then this calculation reverts to:

$$\text{Date of first dose (MP)} - \text{Date of first dose (DBTP)} + 1$$

- During the Maintenance Period (attributed to the treatment initiated in the Maintenance Period), the study medication duration algorithm specified for the Maintenance Period in Section 10.1.2 applies.

- Definitions for time at risk during the combined treatment period will be calculated as follows:

- For study participants who do not switch study treatments per study design:

- For study participants who complete the Maintenance Period as planned and continue into an open-label study (and, therefore, do not have the SFU visit in the feeder study):

$$\text{Date of last visit} - \text{Date of first dose} + 1$$

- For study participants who die prior to the final visit:

$$\text{Date of death} - \text{Date of first dose} + 1$$

- For all other study participants, use the minimum of the following:
 - $Date of last dose - Date of first dose + 140 + 1$
 - $Date of last clinical contact - Date of first dose + 1$

This last group could include study participants who discontinue early, study participants who complete the Maintenance Period as scheduled but choose not to continue into an open-label study, or study participants who are ongoing in the SFU period at the time of the data snapshot.

- For study participants who switch study treatments per study design:

- During the DBTP (attributed to initially randomized treatment):

$$Date of first dose (MP) - 1 - Date of first dose (DPTB) + 1$$

This assumes that any study participant in this category has completed the DBTP and doses [with a new study treatment] in the Maintenance Period.

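### SAP Sections 10.1.1 and 10.1.3 give double-blind time at risk that differs by one day for the same placebo switchers, and the first maintenance dose day is counted in both periods for continuing participants in either arm

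*SAP*

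**What the plan says.** Write D for the date of the first double-blind dose and M for the date of the first maintenance dose.

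- **SAP Section 10.1.1, time at risk.** The rule "For study participants who complete the final visit of the DBTP and continue to the Maintenance Period" is M − D + 1. It applies to both arms. For participants who stop at or before Week 16, the same section uses period lengths of 112 days (stop before the Week 16 visit) or a length based on the Week 16 visit date, "which can be a maximum of 115 days due to visit windows".
- **SAP Section 10.1.3, time at risk in the combined periods.** For participants who switch by design, that is, placebo to bimekizumab, the double-blind part is "Date of first dose (MP) - 1 - Date of first dose (DPTB) + 1", or M − 1 − D + 1. The section adds that anyone in this category is assumed to have completed the double-blind period and been dosed in maintenance.
- **SAP Section 3.2.2.1.1, safety periods.** The double-blind period "Starts on the day of the first IMP administration and ends prior to the day of first IMP administration in the maintenance period". The maintenance period "Starts on the day of IMP administration at the Week 16 visit", or on the first later dose if the Week 16 dose is missed.
- **SAP Section 10.1.2, maintenance time at risk.** For participants who complete and enter the extension it is last visit − M + 1. The other rules there also start counting at M inclusive.
- **SAP Sections 3.7 and 10.2.** Adverse events on the day of the switch are attributed to placebo. Section 3.7 excepts anaphylactic, hypersensitivity, administration-site and injection-site events, which go to bimekizumab.

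**The concern.** Every placebo switcher meets the conditions of both Section 10.1.1 and Section 10.1.3, so one person has two values for one quantity. Both formulas cannot be programmed without producing totals that disagree. Section 10.1.1 also departs from the period definition in Section 3.2.2.1.1 and, taken with Section 10.1.2, counts the boundary day twice.

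Time at risk is the denominator of the exposure-adjusted event rate. For participants without the event of interest, it also feeds the denominator of the exposure-adjusted incidence rate (Section 10.2). The descriptive exposure table in Section 10.1 shows overall and by-period person-time together, which is where a mismatch would be visible. At stake are traceability and internal consistency of the safety denominators, not any efficacy result.

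**Working it through.** **Inputs.** The nominal interval from D to M is 16 × 7 = 112 days. The visit window through Week 16 is ±3 days (Section 3.1). Planned numbers are 200 bimekizumab and 100 placebo (Section 2.3). A subject-year is 365.25 days (Section 10.1).

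**Step 1: reproduce the SAP's own figures.** Section 10.1.1 states 112 days, and 115 at most for those who stop at the Week 16 visit. Counting from D to the day before M, as Section 3.2.2.1.1 defines the period, gives 112 days on schedule and 112 + 3 = 115 with a dose three days late. The Section 10.1.3 formula gives the same values. The Section 10.1.1 formula for continuing participants does not.

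| First maintenance dose | M − D | 10.1.1: M − D + 1 | 10.1.3: M − 1 − D + 1 | Period definition |
|---|---|---|---|---|
| 3 days early | 109 | 110 | 109 | 109 |
| On schedule | 112 | 113 | 112 | 112 |
| 3 days late | 115 | 116 | 115 | 115 |

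The one-day gap does not depend on the date. Relative to the period definition it is 1/112 = 0.89% on schedule.

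**Step 2: double counting.** Take a placebo switcher with Week 16 and Week 52 on schedule who enters the extension. Maintenance time at risk by Section 10.1.2 is 364 − 112 + 1 = 253 days.

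- Sections 10.1.1 + 10.1.2: 113 + 253 = 366 days.
- Section 10.1.3: 112 + 253 = 365 days, which is the number of calendar days from first dose to Week 52 inclusive (364 + 1).

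For a bimekizumab participant on the same schedule, Section 10.1.3 takes last visit − first dose + 1 = 365 days. The two period values again sum to 366. There is no second double-blind formula for this participant, but the boundary day is still in both periods.

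**Step 3: effect on person-time, assuming everyone completes and continues.**

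- 100 placebo: 100 × 113 / 365.25 = 30.94 against 100 × 112 / 365.25 = 30.66 subject-years, a difference of 0.27 before rounding.
- 200 bimekizumab: 61.88 against 61.33, a difference of 0.55.
- All 300: 92.81 against 91.99, a difference of 0.82.

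**Step 4: effect on a rate.** Ten events among 100 placebo completers (a count chosen only for illustration) give 100 × 10 / 30.94 = 32.3 per 100 subject-years against 100 × 10 / 30.66 = 32.6. The incidence rate moves by less than this, because participants with the event contribute only their time to that event.

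**The case against.** **The switch-day rule.** The strongest defence is that Sections 3.7 and 10.2 attribute most adverse events on the switch day to placebo, so the extra day in Section 10.1.1 matches the placebo numerator. Subtracting it would remove from placebo time a day whose events mostly stay with placebo. This bears on how the text is repaired, but it does not remove the conflict. Section 10.1.3 works under the same rule and still subtracts the day. Bimekizumab participants do not switch, so the rule gives no reason for their extra day. Section 10.1.2 counts the day in maintenance in any case.

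**Reach.** The overall-period adverse event tables show only the bimekizumab total column (Table 4–3, Section 10.2), so the 112-day placebo formula has no placebo column there. This stands: the disagreement between the two sections would show mainly in the exposure table.

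**Stronger readings the SAP does not support.**

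- A reader might infer that Section 10.1.1 yields at most 116 days. That holds only if the Week 16 dose is given within its window. If it is missed, M is the next administration; at nominal Week 20 the formula gives 141 days.
- A reader might infer an excess of one day for every participant, or that correcting the formula makes all period times add up to the overall time. Neither follows. For participants who stop in the double-blind period, that period is limited to 112 or 115 days, and their safety follow-up is summarised only in the overall tables (Sections 3.2.2.1.1 and 10). Their periods therefore need not sum to overall time by design.
- A reader might extend the point to the capped rule for exposure duration. That rule also includes the day M, but it is the same in Sections 10.1.1 and 10.1.3, so there is no contradiction. With on-schedule dosing it does not apply: the Week 12 dose on Day 85 plus 28 is Day 113, which is not beyond M, and the duration is 85 − 1 + 28 = 112 days.

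**Conclusion.** The contradiction is real and can be checked from the text alone. For placebo switchers, Sections 10.1.1 and 10.1.3 differ by one day. For continuing participants in either arm, Sections 10.1.1 and 10.1.2 both count the day of the first maintenance dose, against the period definition in Section 3.2.2.1.1.

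It is minor: about 0.9% of double-blind person-time for continuing participants, so double-blind event rates are lower by up to about that proportion. The figures of 113 and 112 days assume a Week 16 dose exactly 112 days after the first dose; the one-day gap does not. The subject-year totals assume no dropout. The shift is in the same direction and of similar size in both arms, so it does not materially affect the comparison between them. The risk differences in Section 10.2.2 use participant counts and are untouched.

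**What to change.** Use one formula for double-blind time at risk in Sections 10.1.1 and 10.1.3 for participants who continue to maintenance. The form already in Section 10.1.3, M − 1 − D + 1, is the natural choice because it agrees with Section 3.2.2.1.1 and with the 112- and 115-day figures in Section 10.1.1.

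Add a sentence that ties the formula to the switch-day attribution rule in Sections 3.7 and 10.2, so that the day is counted once and in the same period as its events. Because the listed exceptions send some switch-day events to bimekizumab and the rest to placebo, the sentence should say which period holds the day and how events attributed to the other treatment are handled.

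Aligning the capped exposure-duration rule in Sections 10.1.1 and 10.1.3 with the same boundary is optional.

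The cost is SAP wording and the matching line of derivation code. Double-blind exposure-adjusted rates would rise by under 1%.

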 - For study participants who discontinue early, the SFU period starts the day after the ET Visit and ends on the day of the SFU Visit or on the last contact date, whichever happens later. In the event that no ET visit is performed, the SFU period starts 29 days after the day of last IMP administration.

Per study protocol, if the Week 52 Visit or ET visit is done \geq 20 weeks after the final dose of IMP, the SFU Visit is not required. In that case, the last contact date (Week 52, ET or earlier if applicable) will be used as end of the SFU period.

Note that an IMP administration is said to be “final” when it refers to the very last IMP taken by the study participant in the study. Otherwise, the IMP administration is said to be “last” for a specific study period.

Safety analyses will be summarized for the DBTP, MP, and Overall Periods. Summaries for the MP will also include the SFU period for study participants that do not enter the OLE or discontinue early in the MP. The SFU period for study participants that discontinue in the DBTP will only be summarized in the Overall Period tables.

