10.1 Extent of exposure

Two summary tables will be created to describe the extent of exposure.

The first table consists of a descriptive summary of study medication duration (in days), total study medication duration in (subject-years), and total time at risk (in subject-years). The information will be presented overall (ie, for the entire treatment period (Double-Blind Treatment Period (DBTP) and Maintenance Period (MP) combined)) as well as by treatment periods.

Study medication duration in subject-years is obtained as study medication in days divided by 365.25. Similarly, total time at risk in subject-years is obtained as total time at risk in days divided by 365.25.

A second summary will be created on the cumulative study medication duration for the overall period, as well as by treatment periods.

- The following time durations categories will be considered for the overall period: ≥ 0 weeks, ≥ 16 weeks, ≥ 24 weeks, ≥ 48 weeks.
- The following time durations categories will be considered for the Double-Blind Treatment Period: ≥ 0 weeks, ≥ 4 weeks, ≥ 8 weeks, ≥ 12 weeks.
- The following time durations categories will be considered for the Maintenance Period: ≥ 0 weeks, ≥ 16 weeks, ≥ 24 weeks, ≥ 36 weeks.

A by-study participant listing of date of first and last dose and the duration of exposure will be performed.

The study medication duration (in days) and the time at risk (in days) are defined depending on the study period of interest. See Section 10.1.1 to Section 10.1.5 for further details.

Throughout this section, date of last clinical contact for each study participant is defined as the maximum of [last visit date including SFU visit, last AE start date (including imputed AE start dates), date of study termination or completion, last date of study drug administration].

10.1.1 Duration of exposure and time at risk in the Double-Blind Treatment Period (DBTP)

- The study medication duration during the DBTP will be calculated as follows:

$$\text{Date of last dose (DBTP)} - \text{Date of first dose (DBTP)} + 28$$

(this formula also applies for study participants who discontinue/lost to follow-up during the DBTP).

- If the date of last dose of the DBTP + 28 days extends to a date beyond the date of first dose of the Maintenance period, then this calculation reverts to:

$$\text{Date of first dose (MP)} - \text{Date of first dose (DBTP)} + 1$$

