The EAIR is defined as the number of study participants (k) with a specific AE adjusted for the exposure and will be scaled to 100 subject-years:

$$\text{EAIR} = 100 \times \frac{k}{\sum_{i=1}^n (T_{\text{Exp}(i)})}$$

where n is the total number of study participants in the respective treatment group, and $T_{\text{Exp}(i)}$ is the time of exposure for each study participant defined as:

- For study participants with the specific AE of interest: years since first dose of the study treatment to the first occurrence for the AE of interest at the level of coding evaluated (see Section 10.1)
- For study participants without the AE: the time at risk in years (see Section 10.1)

Exact Poisson 95% confidence intervals for incidence rates are calculated using the relationship between the Poisson and the Chi-square distribution (Ulm, 1990; Fay and Feuer, 1997):

$$\begin{aligned} LCL &= \frac{\chi^2_{2n,\alpha/2}}{2} \\ UCL &= \frac{\chi^2_{2(n+1),1-\alpha/2}}{2} \end{aligned}$$

where n is the number of study participants with a specific AE for the incidence rate of interest and is the basis for the number of the degrees of freedom for the chi-square quantile for the upper tail probability χ^2 .

The EAER will be the number of AEs including repeat occurrences in individual study participants divided by the total time at risk scaled to 100 subject-years and calculated using:

$$\text{EAER} = 100 \times \frac{N_{AE}}{\sum_{i=1}^n (T_{\text{Risk}(i)})}$$

where N_{AE} is the total number of AEs, n is the total number of study participants and $T_{\text{Risk}(i)}$ is the time at risk in years for each study participant.

No confidence interval will be computed for EAER.

In the following sections, all tables based on “100 subject-years” will include EAIR (with 95% confidence interval) and EAER.

As previously indicated in [Table 4–3](#), the AE summary tables described in Section [10.2.1](#) and Section [10.2.2](#) will be presented:

- on the SS for the overall period, presenting the BKZ 160 mg Total treatment column only.
- on the SS for the Double-Blind Treatment Period for the Week 24 interim analysis only, presenting the Placebo and BKZ 160mg treatment columns.
- and on the MS for the Maintenance Period for the Week 52 interim analysis only, presenting the BKZ 160 mg Total treatment column only.

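### For early discontinuers seen again after the ET visit, double-blind adverse events stop at ET while time at risk can run to Day 112, and later placebo TEAEs reach no standard AE table

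*SAP*

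**What the plan says.** **Event window.** SAP 3.2.2.1.1 states that, for participants who withdraw from the study "prior to start of IMP in the maintenance period, the DBTP ends on the day of the ET Visit". For early discontinuers "the SFU period starts the day after the ET Visit"; if no ET visit takes place, it starts 29 days after the last IMP administration. The same section, repeated at the start of Section 10, adds: "The SFU period for study participants that discontinue in the DBTP will only be summarized in the Overall Period tables".

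**Time at risk.** SAP 10.1.1 says: "For study participants who discontinue on or prior to the final visit of the DBTP (ie, Week 16), use the minimum of the following". One limb is the length of the period: "For those that discontinue prior to the Week 16 visit, use 112 days". The other is the time from first dose to last clinical contact. SAP 10.1 says that the "date of last clinical contact for each study participant is defined as the maximum of" several dates, among them the SFU visit and the last AE start date. Within 10.1.1 a looser remark allows last contact to be taken as the last scheduled visit at the site.

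**Tables.** SAP 10.2 presents the AE summaries "on the SS for the overall period, presenting the BKZ 160 mg Total treatment column only". Section 3.7 and Table 4-3 show the same column. Placebo has a column only in the double-blind AE tables.

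**The concern.** An exposure-adjusted rate needs events and person-time taken over the same window. Here a discontinuer who is followed after ET goes on adding days to the double-blind denominator while any event on those days is assigned to the SFU period. Because the last AE start date counts as contact, a post-ET event can itself lengthen the denominator of a rate from which it is excluded.

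The other periods do not show this split. Maintenance summaries include SFU events, and time at risk there runs up to 140 days after the last dose (10.1.2); the combined period uses the same 140 days (10.1.3). The mismatch lies in the only placebo-controlled period.

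Tabulation is a separate gap. SAP 10.2 treats an event as treatment-emergent until 140 days after the final dose. A TEAE after ET on bimekizumab appears in the Overall tables. The same TEAE in a placebo participant who never switched has no column there and is outside the double-blind tables, so a serious post-ET event on placebo would normally be seen only in a listing.

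**Working it through.** **Inputs.**
- Cap of 112 days (10.1.1), which reproduces as 16 × 7; the stated maximum of 115 days is 112 + 3 days of visit window.
- SFU visit 20 weeks after the final dose (2.3), so 20 × 7 = 140 days, and at most 3 days early (3.1).
- On-schedule double-blind doses at Baseline and Weeks 4, 8 and 12 (Section 7), so Days 1, 29, 57 and 85.
- Event cut-off: the ET day or, without an ET visit, 28 days after the last dose (the day before SFU starts).
- Assumed, because the SAP does not give them: ET 14 or 28 days after the last dose, and the share of an arm that leaves early.

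**One participant who attends the SFU visit.** Earliest SFU day = last dose day + 140 − 3. Credited time = min(112, SFU day). Days at risk on which no double-blind event can count = max(0, 112 − cut-off day).

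| Last dose | Earliest SFU | Credited days | Uncountable, cut-off at dose + 14 | Uncountable, cut-off at dose + 28 |
|---|---|---|---|---|
| Day 1 | Day 138 | 112 | 112 − 15 = 97 | 112 − 29 = 83 |
| Day 29 | Day 166 | 112 | 112 − 43 = 69 | 112 − 57 = 55 |
| Day 57 | Day 194 | 112 | 112 − 71 = 41 | 112 − 85 = 27 |
| Day 85 | Day 222 | 112 | 112 − 99 = 13 | 0 (cut-off Day 113) |

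Every on-schedule SFU visit falls after Day 112, so attending it always gives the full 112 days. With a last dose on Day 29 and ET on Day 57, 55/112 = 49% of the credited time cannot yield an event. The last column also applies when there is no ET visit. If ET is the last contact, time at risk ends at ET and the excess is zero.

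**One arm.** Let a share d leave with ET on day e and all be followed past Day 112, and take 112 days for everyone else. Current person-time is N × 112. Person-time matched to the events is N × [(1 − d) × 112 + d × e]. The EAER is then too low by d × (112 − e)/112. For 100 placebo participants the current denominator is 100 × 112/365.25 = 30.66 subject-years.

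| d | e | Matched subject-years | Dilution |
|---|---|---|---|
| 2% | Day 84 | 30.51 | 0.02 × 28/112 = 0.5% |
| 5% | Day 56 | 29.90 | 0.05 × 56/112 = 2.5% |
| 10% | Day 28 | 28.36 | 0.10 × 84/112 = 7.5% |

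The percentages do not depend on N, so they are the same for 200 bimekizumab participants at equal d and e. In the EAIR, only participants without the event contribute full time at risk, so for an uncommon event the dilution is close to the EAER figure.

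**Tracing a post-ET placebo TEAE.** The double-blind window has closed (3.2.2.1.1). The event belongs to SFU and is sent to the Overall tables only (3.2.2.1.1, Section 10). Those tables carry the BKZ Total column alone (3.7, Table 4-3, 10.2). What remains is the listing of all AEs (10.2.1) and, for a COVID-19 related event, possibly the by-treatment table in 10.2.4.

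**The case against.** The strongest reply is that 112 days is a cap inside a minimum rule, that the remark on the last scheduled site visit may have been meant to stop the clock earlier, and that the Overall tables show bimekizumab only by design. The first part stands for participants whose ET visit is their last contact. The second does not settle the matter: the remark is permissive, it conflicts with the definition that 10.1 sets for the whole section, and an SFU visit can itself be read as scheduled. The third is a legitimate presentation choice, but it leaves events that the SAP calls treatment-emergent without a standard table in one arm.

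Several stronger readings are tempting and the text does not support them.
- A reader might infer that an AE leading to discontinuation is lost. Events up to and on the ET day stay in the double-blind tables.
- A reader might infer that someone who stops IMP but keeps attending has an open double-blind window, with events counted to 140 days after the last dose. 3.2.2.1.1 includes participants withdrawn from IMP in the SFU period and starts it 29 days after the last dose when there is no ET visit. The double-blind end for them should still be stated outright.
- A reader might infer that the safety-topic risk differences in 10.2.2 are diluted too. They divide by participants treated and use no person-time. The event window affects them, but that is a choice of period and not an arithmetic error.
- A reader might infer a bias between arms. Equal dropout and timing give equal dilution; a difference arises only if these differ by arm, and the SAP offers no figure for that.

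**Conclusion.** The point holds in a limited form. For participants who discontinue before Week 16 and have clinical contact after ET, double-blind events and double-blind time at risk end on different days, and the EAIR and EAER are too low. The size is modest: about 0.5% to 7.5% for the EAER over assumed dropout of 2% to 10% with ET between Day 84 and Day 28, and less if some leavers have no contact after ET. Separately, post-ET TEAEs of never-switched placebo participants enter no standard AE table, whatever the dropout rate. The sponsor should correct both, but neither touches the efficacy conclusions or removes events up to the ET visit.

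**What to change.** For participants who never receive maintenance dosing, use one end date for both double-blind events and double-blind time at risk. Either of two routes does this:
- End time at risk in 10.1.1 at the event cut-off in 3.2.2.1.1 (ET day, or 28 days after the last IMP without an ET visit). The rates then stay close to treatment, but post-ET events remain outside the placebo comparison.
- Extend the double-blind period in 3.2.2.1.1 to the end of time at risk, and move the SFU start to the following day; otherwise the two periods would overlap. Some off-treatment time then enters the event count, as it already does the denominator.

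With either route:
- State the double-blind end for participants who stop IMP but remain in the study.
- Reconcile the site-visit remark in 10.1.1 with the definition of last clinical contact in 10.1, and bring Table 4-3, which describes double-blind AE tables as running up to Week 16 for each participant, into line.
- Tabulate later TEAEs of never-switched placebo participants in a placebo column or a small separate table.

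The cost is SAP wording, one derivation and one extra column or table. Study conduct does not change.
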